19.4. Descriptive Statistics

All continuous variables will be summarized by cohort and time point with descriptive statistics (the number of nonmissing values, mean, SD, median, minimum, and maximum). All categorical variables will be summarized by cohort and time point with frequency counts and percentages. Treatment group refers to all dose cohorts of ALXN1210.

19.5. Demographics, Baseline Characteristics, and Subject Disposition

All subjects will be included in the summary of subject disposition, which will summarize the frequency and percentage of subjects screened and treated who completed or discontinued from the study, along with reason for discontinuation, by treatment group. Demographics and baseline characteristics will be summarized for all subjects by each treatment dose and overall.

19.6. Safety Analysis

Safety analyses will be performed on the safety population, and will be reported by each treatment dose. Safety analyses will include an analysis of all AEs, ECGs, clinical laboratory data, physical examinations, and vital sign measurements and will be presented using descriptive statistics. No inferential statistical analyses are planned on the safety parameters of this study. The incidence of treatment-emergent AEs and SAEs will be summarized by system organ class and preferred term for each treatment dose and overall, by severity, and by relationship to study drug. Serious AEs and AEs resulting in withdrawal from the study will be listed. Subjects having multiple AEs within a category (eg, overall, system organ class, preferred term) will be counted once in that category. For severity tables, a subject's most severe event within a category will be counted.

Changes from baseline in vital signs and laboratory assessments (chemistry, CBC with differential, and urinalysis) will be summarized by each treatment dose. Laboratory parameter values will be graded according to the National Cancer Institute Common Terminology Criteria for Adverse Events (CTCAE; v4.03, published June 14, 2010). Shift tables by treatment group will be produced for these laboratory parameters. These tables will summarize the number of subjects with each baseline grade relative to the normal ranges and changes to the worst highest grade assessed postdose during the study.

The ECG parameters will be measured at the specified time points, including heart rate, PR, RR, QRS, QT, and corrected QTcF intervals. The average of the triplicate ECG readings at the time points collected will be calculated, and changes from pretreatment baseline values will be assessed by each treatment dose.

An outlier analysis will be performed that will summarize the frequency and percentage of subjects who meet any of the following outlier criteria at each visit by treatment group:

- OT, OTcF interval > 450 msec
- QT, QTcF interval > 480 msec
- QT, QTcF interval > 500 msec
- QT, QTcF interval increases from baseline > 30 msec
- QT, QTcF interval increases from baseline > 60 msec

All concomitant medications will be coded using the WHO Drug Dictionary, and the frequency and percentage of concomitant medications will be summarized.

19.7. Pharmacokinetic Analysis

The individual serum concentration data for ALXN1210-treated subjects, with actual sampling dates and times, will be used to derive the PK parameters by noncompartmental analyses using Phoenix WinNonlin 6.3 or higher.

The following PK parameters will be derived: maximum observed serum concentration (C_{max}) after each dose, time to maximum observed serum concentration (t_{max}), the observed minimum serum concentrations (C_{min}) just prior to Periods 2 to 5 (and 28 days after Period 5 dose) for Cohort 3, area under the serum concentration versus time curve from time 0 to the last quantifiable concentration (AUC_t) after each dose, area under the curve from time 0 (dosing) to the end of the dosing interval (AUC_t), apparent terminal-phase elimination rate constant (λ_z), terminal elimination half-life ($t_{1/2}$), total clearance (CL), volume of distribution (V_{ss}), assessment of steady-state, and accumulation at steady state. Assessment of dose proportionality and time linearity in PK parameters may be conducted.

19.8. Pharmacodynamic and Immunogenicity Analyses

The PD effects of ALXN1210 administered intravenously will be evaluated by assessing changes in serum total and free C5 concentrations, cRBC hemolysis, and other measures of C5 activation over time. Analyses will be initially performed on samples collected as described in the Schedules of Assessments (Section 9).

An exploratory PK/PD analysis may be performed.

Immunogenicity, as measured by ADA, will be summarized in tabular form by treatment dose and by-subject listings.

19.9. Interim Analysis

Interim analyses may be performed as needed.

20. DIRECT ACCESS TO SOURCE DATA/DOCUMENTS

20.1. Study Monitoring

Before an investigational site can enter a subject into the study, a representative of Alexion (sponsor) will visit the investigational study site to:

- Determine the adequacy of the facilities;
- Discuss with the investigator(s) and other personnel their responsibilities with regard to protocol adherence, and the responsibilities of the sponsor or designee.

During the study, a monitor from the sponsor or designee will have regular contact with the investigational site, for the following:

- Provide information and support to the investigator;
- Confirm that facilities remain acceptable;
- Confirm that the investigational team is adhering to the protocol, that data are being accurately recorded in the case report form, and that investigational product accountability checks are being performed;
- Perform source data verification. This includes a comparison of the data in the case report form with the subject's medical records at the hospital or practice, and other records relevant to the study. This will require direct access to all original records for each subject (eg, clinic charts);
- Record and report any protocol deviations not previously sent to the sponsor or designee;
- Confirm AEs and SAEs have been properly documented in the case report form, and confirm any SAEs have been forwarded to the sponsor or designee, and those SAEs that met criteria for reporting have been forwarded to the IRB/IEC.

The monitor will be available between visits if the investigator(s) or other staff needs information or advice.

20.2. Audits and Inspections

Authorized representatives of the sponsor or designee, a regulatory authority, or an IRB/IEC may visit the site to perform audits or inspections, including source data verification. The purpose of an audit or inspection is to systematically and independently examine all study-related activities and documents to determine whether these activities were conducted, and data were recorded, analyzed, and accurately reported, according to the protocol, Good Clinical Practice (GCP) guidelines of the International Conference on Harmonisation (ICH), and any applicable regulatory requirements. The investigator should contact the sponsor or designee immediately if contacted by a regulatory agency about an inspection.

20.3. Institutional Review Board/Independent Ethics Committee

The investigator must obtain IRB/IEC approval for the clinical study. Initial, subsequent, and ongoing IRB/IEC approvals, and all materials approved by the IRB/IEC for this study, including the subject consent form and recruitment materials, must be maintained by the investigator and made available for inspection.

20.4. Safety Review Committee

Since its primary function will be to ensure subject safety, the members of the SRC will have access to all safety data. For additional details regarding the SRC, please see Section 8.5.

20.5. Regulatory Agency

As required by the United Kingdom regulatory agency, a Clinical Trial Application will be submitted before the beginning of the study and a Notice of Acceptance Letter must be received prior to screening.

21. QUALITY CONTROL AND QUALITY ASSURANCE

To ensure compliance with GCP and all applicable regulatory requirements, the sponsor or designee may conduct a quality assurance audit. Please see Section 20.2 for more details regarding the audit process.

22. ETHICS

22.1. Ethics Review

The final study protocol and the final version of the ICF must be approved or given a favorable opinion in writing by an IRB/IEC, as appropriate. The investigator must submit written approval to the sponsor or designee prior to enrolling subjects.

The investigator is responsible for informing the IRB/IEC of any amendment to the protocol, in accordance with local regulatory requirements. The IRB/IEC must review and approve any protocol amendments prior to implementation at the study site. The IRB/IEC will review the protocol at least annually or as local regulations require. In addition, the IRB/IEC must approve all advertising used to recruit subjects for the study.

The investigator is also responsible for informing the IRB/IEC of any reportable serious adverse drug reactions from any other study conducted with the investigational product. The sponsor or designee will provide this information to the investigator.

Progress reports and notifications of serious adverse drug reactions will be provided to the IRB/IEC, according to local regulations and guidelines.

22.2. Ethical Conduct of the Study

The study will be performed in accordance with ethical principles that have their origin in the Declaration of Helsinki and are consistent with ICH, GCP, applicable regulatory requirements, and Alexion's policy on bioethics.

22.3. Written Informed Consent

The investigator will ensure that the subject is given full and adequate oral and written information about the nature, purpose, possible risk, and benefit of the study. Subjects must also be notified that they are free to discontinue from the study at any time. The subject should be given the opportunity to ask questions and allowed time to consider the information provided.

The subject's signed and dated ICF must be obtained before conducting any study procedures, and documented in the subject's study record.

The investigator must maintain the original of all signed ICF versions. A copy of the signed ICF(s) must be given to the subject.

22.4. Urgent Safety Measures

If an event occurs that is related to the conduct of the study or the development of the study drug, and this new event is likely to affect the safety of subjects, the sponsor and the investigator will take appropriate urgent safety measures to protect subjects against any immediate hazard. The sponsor will work with the investigator to ensure the IRB/IEC is notified. The sponsor will also inform the Medicines and Healthcare Products Regulatory Agency.

23. DATA HANDLING AND RECORDKEEPING

23.1. Inspection of Records

The sponsor or designee will be allowed to conduct site visits to the investigation facilities for the purpose of monitoring any aspect of the study. The investigator agrees to allow the monitor to inspect the drug storage area, study drug stocks, drug accountability records, subject charts, and study source documents, and other records relative to study conduct.

23.2. Retention of Records

The clinical site will maintain adequate study records according to local regulatory requirements after completion or termination of study or for a minimum period of 5 years. After that period, the sponsor will be contacted to determine whether the study records will be forwarded to the sponsor, destroyed, or kept at the clinical site or another facility for a longer period of time, at the sponsor's expense. If it becomes necessary for the sponsor or designee or the regulatory authority to review any documentation relating to the study, the investigator must permit access to such records.

24. PUBLICATION POLICY

The terms for publication are outlined in the Clinical Study Agreement, Statement of Agreement, or the Master Clinical Study Agreement. Refer to these documents for further details and information.

[figure not shown]

26. APPENDICES

26.1. Appendix 1

[figure not shown]
Acute Infusion Reactions Algorithm

^{*} National Cancer Institute Common Terminology Criteria (NCI CTC) for AEs (NCI CTCAE, version 4.0)

26.2. Appendix **2**

United Kingdom Resuscitation Council Anaphylaxis Algorithm

(IM or slow IV)

10 mg

5 mg

2.5 mg

250 micrograms/kg

Adult or child more than 12 years

Child 6 - 12 years

Child 6 months to 6 years

Child less than 6 months

(IM or slow IV)

200 mg

100 mg

50 mg

25 mg

## LIST OF ABBREVIATIONS AND DEFINITIONS OF TERMS

Abbreviation or	Explanation
	apparent terminal elimination rate constant
	apparent terminal- emmation rate constant
	adverse event
	area under the corum concentration versus time curve from time
AUC∞	A extrapolated to infinity
	area under the serum concentration versus time curve from time
AUCE	A to the last quantifiable concentration
	area under the serum concentration versus time curve from time
	0 to the end of the dosing interval (tau)
BLO	below the level of quantification
BMI	body mass index
CI	total body clearance
Cmax	maximum observed serum concentration
Cmin	minimum observed serum concentration
CSR	clinical study report
cRBC	chicken red blood cell
CV	coefficient of variation
ECG	electrocardiogram
IMP	Investigational Medicinal Product
IV	intravenous
LLO	lower limit of quantification
MedDRA	medical dictionary for regulatory activities
PD	pharmacodynamic(s)
PI	principal investigator
РК	pharmacokinetic(s)
PT	preferred term
QTcB	QT interval corrected using Bazett's formula
QTcF	QT interval corrected using Fridericia's formula
R	accumulation ratio
RPL	Richmond Pharmacology Ltd
SAE	serious adverse event
SAP	statistical analysis plan
SAS	statistical analysis software
SD	standard deviation
SOC	system organ class
SRC	safety review committee
TEAE	treatment-emergent adverse event
TFL	tables figures and listings
t1/2	terminal elimination half-life
t max	time to maximum observed serum concentration
Vss	volume of distribution at steady state
WHO	world health organization

### 1. INTRODUCTION

The purpose of this Statistical Analysis Plan (SAP) is to define the variables and analysis methodology to address the study objectives.

Final Protocol Amendment 1 dated 24 Aug 2016 was used in the preparation of this SAP.

Pharmacokinetic parameters will be calculated by Alexion or its designee. Richmond Pharmacology Ltd (RPL) is responsible for performing statistical analyses. Tables, figures, and listings will be produced using Statistical Analysis Software (SAS) V9.2 or higher.

## 2. STUDY OBJECTIVES AND ENDPOINTS

#### 2.1 Study objectives

The objectives of this study are:

#### Primary

• To evaluate the safety and tolerability of single and multiple doses of ALXN1210 following intravenous (IV) administration to healthy Japanese subjects.

#### Secondary

- To investigate the immunogenicity of ALXN1210 in healthy Japanese subjects.
- To characterize the pharmacokinetics (PK) of single and multiple doses of ALXN1210 in healthy Japanese subjects.
- To evaluate the pharmacodynamics (PD) effects of ALXN1210 as assessed by total and free C5 concentrations and chicken red blood cell (cRBC) hemolysis in healthy Japanese subjects.

#### 2.2 Endpoints

Safety, immunogenicity, PK, and PD endpoints are described in the sections to follow. Timing of assessments is displayed in the Schedules of Assessments.

#### Safety Endpoints

Safety endpoints include the following:

- Change from baseline in physical examination assessments
- Change from baseline in vital signs
- Incidence of antidrug antibody (ADA) measured via immunogenicity testing
- Change from baseline in electrocardiogram (ECG) parameters
- Change from baseline in laboratory measurements
- Incidence of Adverse Events (AE) and Serious Adverse Events (SAE)

#### Pharmacokinetic Endpoints

The following PK parameters will be evaluated:

- Observed maximum serum concentration following all ALXN1210 doses (Cmax) following single dose (Cohort 1 and 2) and doses 1 and 5 (Cohort 3);
- Dose-normalized  $C_{max}$ , following single dose (Cohort 1 and 2) and doses 1 and 5 (Cohort 3);
- Time to maximum observed serum concentration (tmax) following single dose (Cohort 1 and 2) and doses 1 and 5 (Cohort 3);
- Trough serum concentrations (Ctrough) just prior to Doses 2 to 5, and 28 days after the 5th dose (Cohort 3);
- Area under the serum concentration versus time curve from time 0 to the last quantifiable concentration (AUCt) after single dose (Cohort 1 and 2) and after dose 5 (Cohort 3);
- Dose-normalized AUCt after single dose (Cohort 1 and 2) and following dose 5 (Cohort 3);
- AUC from time 0 (dosing) to the end of the dosing interval (AUC $\tau$ ) following doses 1 and 5 (Cohort 3). Following Dose 5, calculated over dosing interval (28 days);
- Terminal-phase elimination rate constant ( $\lambda_z$ ) after single dose (Cohort 1 and 2) and after dose 5 (Cohort 3);
- Terminal elimination half-life (t/2) after single dose (Cohort 1 and 2) and after dose 5 (Cohort 3);
- Total body clearance of drug from the serum (CL) after single dose (Cohort 1 and 2) and after dose 5 (Cohort 3);
- Volume of distribution at steady state (Vss) (Cohort 3);
- Assessment of steady state (Cohort 3);
- Accumulation at steady state (R) after the fifth dose (Cohort 3).

## Pharmacodynamic Endpoints

Pharmacodynamic effects will be evaluated as follows:

- Change in serum total and free C5 concentration over time
- Change in cRBC hemolysis over time
- ALXN1210 concentration required for complete terminal complement inhibition based on PD effects evaluated.

## 3. NUMBER OF SUBJECTS AND RANDOMIZATION

## 3.2 Number and Source of Subjects

Up to 16 subjects are planned for evaluation of the primary and secondary objectives, and a maximum of 22 subjects could be enrolled and dosed. The total number of subjects dosed (including potential added subjects) will remain within a maximum of 6 subjects each in Cohorts 1 and 2 and 10 subjects in Cohort 3, for a maximum of 22 subjects in this study.

## 3.3 Randomization and Blinding

This is an open-label study (subjects and on-site medical/nursing staff and pharmacy staff are aware of study drug/dose assignment). Eligible subjects who meet the inclusion/exclusion criteria will be sequentially enrolled and assigned to

receive ALXN1210. Once a subject identification number has been assigned to 1 subject, it may not be assigned to another subject.

### 4. STATISTICAL ANALYSES

In general, descriptive statistics for continuous variables will include number of non-missing values, mean, standard deviation (SD), median, minimum, and maximum, by treatment group.

Descriptive statistics for PK parameters will include number of observations, arithmetic mean, SD, arithmetic coefficient of variation (CV), geometric mean, geometric CV, median, minimum and maximum, by treatment group.

Descriptive statistics for PD parameters will include number of observations, arithmetic mean, SD, median, minimum, and maximum, by treatment group.

Categorical variables will be summarized using frequency counts and percentages by treatment group.

Treatment group refers to all dose cohorts of ALXN1210.

Baseline will be defined as the last value of the assessment recorded prior to first administration of Investigational Medicinal Product (IMP). For post-dose assessments the first scheduled value will be used for summary analysis if repeated measurements are made at a time-point.

Deviations from the planned analyses will be described in the final integrated clinical study report.

#### 4.1. Analysis Populations

The safety population will consist of all subjects who receive at least 1 dose of study drug. Subjects in this population will be used for the safety analysis.

The PK population will consist of all subjects who have sufficient serum concentration data to enable the calculation of PK parameters. The PK population will be used for PK analysis.

The PD population will consist of all subjects who have sufficient total and free C5 concentration data and cRBC hemolysis data. The PD population will be used for PD analysis.

The immunogenicity analysis population will consist of all subjects who have a pre-dose and post-dose ADA samples collected.

Inclusion and exclusion from each analysis set will be decided at the Data Review Meeting prior to database lock.

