14.2. Criteria for Evaluation

All subjects providing PD samples will be included in the PD analysis population.

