19.2. Analysis Populations

The safety population will consist of all subjects who receive at least 1 dose of study drug. Subjects in this population will be used for the safety analysis.

The PK population will consist of all subjects who have sufficient serum concentration data to enable the calculation of PK parameters. The PK population will be used for PK summaries.

The PD population will consist of all subjects who have sufficient total and free C5 concentration data, cRBC hemolysis data, or other data measuring C5 activation to enable the evaluation of the PD effects. The PD population will be used for PD summaries.

The immunogenicity analysis population will consist of all subjects who have a predose and postdose ADA sample collected.

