#### 4.7. Pharmacodynamic Analyses

The PD effects of ALXN1210 administered IV will be evaluated as follows:

- Changes and percent changes in serum Total C5 and Free C5 concentration over time.
- Change and percent change in cRBC hemolysis over time.
- ALXN1210 concentration required for complete terminal complement inhibition based on PD effects evaluated.

PD data will be listed for each individual subject and absolute (observed values) as well as changes and percent changes from baseline will be summarized at each time point by treatment dose using the following descriptive statistics.

- N (the number of subjects)
- Arithmetic mean
- SD
- Median
- Minimum
- Maximum.

Individual percent change from baseline versus actual time and mean percent change from baseline versus nominal time will be presented for each PD parameter.

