## 5. CONVENTIONS

All listings will be ordered by treatment and subject number and will include all enrolled subjects. All data will be presented by the dose level of treatment.

For all tables, except PK parameter tables, descriptive statistics for min, max will be presented with the same number of decimal digits as the original values, and with one more decimal digit than the original data for mean and median; standard deviation will be reported with 2 or more decimal digits than the original.

For PK, the individual and summaries of PK parameter results will be reported in 3 significant digits in the listings and in the tables with the following exceptions:

- Tmax will be presented as follows: individual minimum, and maximum values will be reported exactly as the raw data are reported
- % CV will be presented to 1 decimal place

Page layout of tables and listings in landscape mode will be produced in Microsoft Word. Details of page layout will be provided in the tables figures and listings (TFL) shell document.

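### SAP 4.1 requires both C5 and cRBC hemolysis data to enter the single PD population, while the protocol accepts either (19.2) or any PD sample (14.2)

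*SAP*

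**What the plan says.** Three definitions of the PD population are in force.

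- **Protocol 14.2:** "All subjects providing PD samples will be included in the PD analysis population". No sufficiency condition is attached.
- **Protocol 19.2:** subjects need sufficient data of one of several kinds. The list opens with total and free C5 concentrations and ends "cRBC hemolysis data, or other data measuring C5 activation to enable the evaluation of the PD effects".
- **SAP 4.1:** "all subjects who have sufficient total and free C5 concentration data and cRBC hemolysis data". The route through other C5-activation data is gone.

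SAP 4.1 then makes this one population serve everything: "The PD population will be used for PD analysis". Membership is settled late: "Inclusion and exclusion from each analysis set will be decided at the Data Review Meeting prior to database lock". *Sufficient* is not defined for PD in either document.

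SAP Section 1 says the SAP was prepared from Protocol Amendment 1, which is the version that contains 14.2 and 19.2. It gives no reason for a narrower definition.

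**The concern.** C5 concentration and cRBC hemolysis are separate PD endpoints in Protocol 7.3 and SAP 2.2. Nothing in the plan makes a C5 summary depend on hemolysis data. Under SAP 4.1 as written, however, a shortfall in one read-out removes the subject from the summaries of the others.

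PD evaluation is a secondary objective. Protocol 8.3 also says that PD data from this study will be compared with the two non-Japanese studies for bridging. With four subjects in each single-dose cohort, losing a valid profile for an unrelated reason is a real cost. The PD tables would also rest on a population that differs from either protocol definition, with no explanation given.

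**Working it through.** The plan states no figure on this point, so the check compares the texts and then sizes one exclusion.

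**1. Apply each definition to two subjects.** Subject A has sufficient total and free C5 data but insufficient hemolysis data. Subject B is the reverse. Neither has other C5-activation data.

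| Definition | Joining rule | A | B |
|---|---|---|---|
| Protocol 14.2 | any PD sample | in | in |
| Protocol 19.2 | C5, or cRBC, or other | in | in |
| SAP 4.1 | C5 and cRBC | out | out |

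The two protocol definitions agree on A and B. The SAP disagrees with both.

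**2. See what the exclusion reaches.** SAP 4.7 gives the read-outs separate entries. One is "Changes and percent changes in serum Total C5 and Free C5 concentration over time" and the next is the change in cRBC hemolysis. Because SAP 4.1 sets one population for all PD analysis, A leaves the C5 summaries and B leaves the hemolysis summaries. It does not reach the listings. SAP Section 5 says: "All listings will be ordered by treatment and subject number and will include all enrolled subjects".

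**3. Size one exclusion.** Planned cohort sizes (Protocol 19.3, SAP 4.2) are 4, 4, and 6 to 8. The share lost from the unaffected read-out is 1/n. At an unchanged SD, the standard error of a cohort mean grows by √(n/(n−1)).

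| Cohort | n | Share lost | Standard error factor |
|---|---|---|---|
| 1 or 2 | 4 to 3 | 1/4 = 25% | √(4/3) = 1.155 |
| 3, smallest | 6 to 5 | 1/6 = 16.7% | √(6/5) = 1.095 |
| 3, largest | 8 to 7 | 1/8 = 12.5% | √(8/7) = 1.069 |

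The last column is illustrative, because the SAP plans only descriptive PD statistics.

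**4. What cannot be computed.** The SAP and Protocol 19.2 differ only for subjects whose sufficiency differs between read-outs. The documents give no rate for this. If every loss hit all read-outs together, SAP 4.1 and Protocol 19.2 would give the same population and the effect would be zero.

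**The case against.** The case for leaving the text alone has substance.

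- **Sufficient does not mean complete.** Counting the PD tables in Protocol 14.1 gives 20 scheduled samples per subject in Cohort 1, 21 in Cohort 2 and 60 in Cohort 3 (12 + 3 × 9 + 21). One failed run costs a time point, which SAP 4.9 leaves unimputed. A reader might infer that any single assay failure removes the subject. The documents do not support that: the read-out must be judged insufficient for the subject as a whole.
- **Losses may be shared.** The read-outs form one PD panel with the same sampling times, so a missed visit or a withdrawal affects all of them. That they fail independently is nowhere stated, so a failure probability per cohort would rest on invented rates.
- **Results are not wholly lost.** A reader might say the subject vanishes from every PD result. The listings rule prevents that.
- **Discretion is not peculiar to *and*.** Protocol 19.2 also relies on undefined sufficiency, and the Data Review Meeting decides every analysis set. The narrower rule cannot be blamed for data-dependent exclusion in general.
- **Reporting limits the harm.** SAP 4.7 already gives N at each time point, SAP Section 4 sends deviations from planned analyses to the study report, and SAP 4.9 allows missing-data methods to be reassessed before lock.
- **No PD sample size is promised.** Dropping the other-data route also fits the listed PD endpoints, since Protocol 14.1 treats further C5 measures only as a possibility.

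All of this stands, and it limits how likely and how large the effect is. None of it makes the SAP's rule equal to the protocol's, or gives a reason to tie C5 summaries to hemolysis data. A sensible review meeting might never apply the strict reading, but then it would be departing from the SAP's text.

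**Conclusion.** The contradiction is real and should be corrected before database lock. Its effect is conditional and limited to descriptive summaries of a secondary objective. If one subject has sufficient data on one read-out but not on the other, the literal SAP rule costs the sound read-out a quarter of a single-dose cohort, or between an eighth and a sixth of Cohort 3. This rests on three things: the SAP being applied as written, cohorts at their planned sizes, and one such subject in the cohort. How often that would occur is unknown from the documents. The fault is the joining rule and the single population. It is not evidence that exclusions would be driven by results, nor that PD data would go unreported.

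**What to change.** In SAP 4.1, replace the *and* between C5 and cRBC hemolysis data with the protocol's *or*. Add that total C5, free C5 and cRBC hemolysis are each summarised on the subjects with evaluable data for that read-out. The addition is needed because both documents still join total and free C5 with *and*, so *or* alone would not separate those two.

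Define *evaluable* in the same place. A baseline and at least one post-dose value would serve. That criterion is a suggestion and not existing protocol text, though it resembles the pre-dose and post-dose rule that SAP 4.1 already uses for immunogenicity.

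At the next amendment, give Protocol 14.2 and 19.2 the same sentence so that one definition remains.

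The cost is about a sentence in each place. The n may differ between PD tables, which the planned N per time point already makes visible. The protocol edit needs ethics committee approval before implementation (Protocol 22.1); the SAP edit need not wait for it.
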